Radiographic Tumor Assessment (Chest, Abdomen, Head)	X	Within 28 days prior to first dose. CT/MRI of brain (with contrast, unless contraindicated) required for subjects who have known history of brain metastases or if clinically indicated.. Additional sites of known or suspected disease (including pelvis) should be imaged at the screening visit.
Archived Tumor Tissue or Recent Tumor Biopsy	X	
One formalin-fixed paraffin embedded tumor tissue block, or 10 minimum FFPE unstained slides are to be submitted if available. Submit a copy of the original pathology report along with the sample. Tissue samples from different biopsy procedures are to be submitted if available with each matching pathology report and biopsy date.
 
NOTE: For subjects previously enrolled in CA 209118, tumor tissue and/or laboratory data generated from tissue collected in CA209118 is to be utilized for this study.

Table 5.1-2: On-Study Procedural Outline (CA209153)

Procedure	C1D1 (Cycle 1 Day 1)	Each Cycle (Every 2 weeks) on Day 1	Every 3 Cycles (Every 6 weeks) on Day 1	Every 4 Cycles (Every 8 weeks) on Day 1	Notes
Safety Assessments					
Vital Signs and oxygen saturation ^a	X	X			Within 72 hours prior to dosing. Include temperature, blood pressure, heart rate, respiratory rate, oxygen saturation by pulse oximetry at rest prior to dosing and at any time there are new or worsening respiratory symptoms. (see Section 5.3.2) Patients randomized to Cohort B will be assessed every 2 or 4 weeks for clinical assessment and physical examination per investigator decision. If nivolumab is restarted, every two week assessment schedule must be resumed.
Adverse Events Assessment			Continuously		Continuously assessed using NCI CTCAE v. 4.0.
Physical measurements and target physical exam (including Performance Status)	X	X			Includes weight, ECOG status, and targeted physical exam as clinically indicated Patients randomized to Cohort B will be assessed every 2 or 4 weeks for clinical assessment and physical examination per investigator decision. If nivolumab is restarted, every two week assessment schedule must be resumed.
Laboratory Tests^b					Cohort B: For subjects randomized to Cohort B, lab tests will be performed every 4 weeks. If nivolumab is restarted, every two week lab assessment schedule must be resumed.

Table 5.1-2: On-Study Procedural Outline (CA209153)

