Procedure	C1D1 (Cycle 1 Day 1)	Each Cycle (Every 2 weeks) on Day 1	Every 3 Cycles (Every 6 weeks) on Day 1	Every 4 Cycles (Every 8 weeks) on Day 1	Notes
Complete blood counts (CBC) (Obtain results prior to dosing on infusion days)	X	X			Screening labs performed within 14 days of C1D1 visit do not need to be repeated unless clinically indicated. For C2D1 and beyond, to be performed within 72 hours prior to dosing. Tests include WBC count with differential, lymphocyte count, ANC, hemoglobin, hematocrit, and platelet count
Serum chemistry (Review results prior to dosing on infusion days)	X	X			Screening labs performed within 14 days of C1D1 visit do not need to be repeated unless clinically indicated. For C2D1 and beyond, to be performed within 72 hours prior to dosing. BUN or serum urea level, serum creatinine, sodium, potassium, calcium, magnesium, phosphate, chloride, glucose, and LDH
Liver function (Review results prior to dosing on infusion days)	X	X			Screening labs performed within 14 days of C1D1 visit do not need to be repeated unless clinically indicated. For C2D1 and beyond, to be performed within 72 hours prior to dosing. Aspartate aminotransferase (AST), alanine aminotransferase (ALT), total bilirubin, alkaline phosphatase, albumin
Thyroid function	X		X*		Screening labs performed within 28 days of C1D1 visit unless clinically indicated. TSH (reflex to free T3 and free T4 if abnormal result) Thyroid function test may be performed within 72 hours prior to dosing. *Cohort B: TSH/thyroid function tests can be done every 12 weeks.

Table 5.1-2: On-Study Procedural Outline (CA209153)

Procedure	C1D1 (Cycle 1 Day 1)	Each Cycle (Every 2 weeks) on Day 1	Every 3 Cycles (Every 6 weeks) on Day 1	Every 4 Cycles (Every 8 weeks) on Day 1	Notes
Pregnancy Test	X		X		Serum or urine test for WOCBP only, to be performed C1D1 and every 6 weeks, or more frequently as required by local standards. Serum or urine test may be performed within 24 hours of scheduled dose.
Review of concomitant medications	X	X			At each visit
Efficacy Assessments					

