8.4.3 Secondary Analyses

The number and percentage of subjects who report high grade (Grade 3-4 and Grade 5) select adverse events will be summarized for all treated subjects. High grade (Grade 3-4 and Grade 5) select adverse events will be tabulated using worst grade per NCI CTCAE v4.0 criteria by system organ class and Medical Dictionary for Regulatory Affairs (MedDRA) preferred term.

Additional descriptive statistics will include median values using the Kaplan-Meier (KM) product-limit method with 95% CI using Brookmeyer and Crowley method of time to onset and time to resolution, and will be presented for all treated subjects, by tumor histology (SQ or NSQ), by subject subgroups, and all randomized subjects for Cohorts A and B. Time to onset is calculated from first dosing date to the event onset date. If a subject never experienced the given AE, the subject will be censored at the last contact date. Time to resolution is calculated from the

AE onset date to AE end date. If an AE is ongoing at the time of analysis, the time to resolution will be censored at the last contact date.

Management of high-grade (CTCAE v4.0 Grade 3-4 and Grade 5) select adverse events will be characterized by measuring percentage of subjects who received immune modulating medication (or hormonal replacement therapy), percentage of subjects who received ≥ 40 mg prednisone equivalents, and total duration of all immune modulating medications given for the event, in all treated subjects who have experienced high-grade (CTCAE v4.0 Grade 3-4 and Grade 5) select adverse events, by tumor histology (SQ or NSQ), and also by subject subgroups, and all randomized subjects in Cohorts A and B.

8.4.4 *Exploratory Analyses*

8.4.4.1 *Safety Analyses:*

All safety data will be summarized and listed for all treated subjects. All on-study AEs, SAEs, treatment-related AEs, and treatment-related SAEs will be summarized using worst grade per NCI CTCAE v4.0 by system organ class and preferred term. On-study lab abnormalities including hematology, chemistry, liver function, thyroid function, and renal function will be summarized using worst grade per NCI CTCAE v4.0 criteria.

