Descriptive statistics of safety (AE and lab data) including incidence, median values using the Kaplan-Meier (KM) product-limit method with 95% CI using Brookmeyer and Crowley method of time to onset and time to resolution, and rate of discontinuation due to event occurrence will be presented for all treated subjects, by tumor histology (SQ or NSQ), by subject subgroups, and all randomized subjects for Cohorts A and B. Time to onset is calculated from first dosing date to the event onset date. If a subject never experienced the given AE, the subject will be censored at the last contact date. Time to resolution is calculated from the AE onset date to AE end date. If an AE is ongoing at the time of analysis, the time to resolution will be censored at the last contact date.

8.4.4.2 *Efficacy Analyses*

[figure not shown]
OS and PFS will be summarized by KM product-limit method for all treated subjects and all response evaluable subjects, respectively. Median values of OS and PFS, along with two-sided 95% CI using Brookmeyer and Crowley method, will be calculated. Survival rates at 6, 12, 18 and 24 months will also be estimated using KM estimates on the OS curve for all treated subjects. Associated two-sided 95% CIs will be calculated using the Greenwood formula. This analysis will be performed for all treated subjects or for all response evaluable subjects for PFS. This analysis will also be performed by tumor histology (SQ or NSQ), by subject subgroups, and all randomized subjects for Cohorts A and B.

The ORR will be summarized by binomial response rates and their corresponding two-sided 95% exact CIs using the Clopper-Pearson method. This analysis will be performed for all response evaluable subjects. This analysis will also be performed by tumor histology (SQ or NSQ), by subject subgroups, and all randomized subjects for Cohorts A and B.

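### While Cohort A is on nivolumab and Cohort B is off it, A has scheduled laboratory tests about twice as often, and the by-cohort laboratory summaries make no allowance for this

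*Combined protocol and SAP*

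**What the plan says.** **Schedule.** Table 5.1-2 places blood counts, chemistry and liver function under "Each Cycle (Every 2 weeks) on Day 1" and thyroid function under "Every 3 Cycles (Every 6 weeks) on Day 1". Cohort A stays on this schedule while it is treated. For Cohort B the notes say "For subjects randomized to Cohort B, lab tests will be performed every 4 weeks" and, for thyroid function, "TSH/thyroid function tests can be done every 12 weeks". The second is a permission, not a requirement. On retreatment the difference ends: "If nivolumab is restarted, every two week lab assessment schedule must be resumed".

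**Analysis.** Section 8.4.4.1 says "On-study lab abnormalities including hematology, chemistry, liver function, thyroid function, and renal function will be summarized using worst grade". That paragraph is written for all treated subjects and does not name the cohorts. The next paragraph does. It covers adverse-event and laboratory data together and asks for incidence, Kaplan-Meier medians of time to onset and resolution, and discontinuation rates. It says "rate of discontinuation due to event occurrence will be presented for all treated subjects", and the same sentence goes on to histology, subgroups and all randomised subjects in Cohorts A and B. Onset is counted from the first dose. Section 8.2 plans subpopulation analyses by cohort, and Section 1.3.3 includes laboratory abnormalities in Cohorts A and B in an exploratory objective.

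Section 8.3.3 describes laboratory testing as done at the start of each cycle, as if one schedule applied to everyone. Nothing in the readable text of Section 8 limits the cohort summaries to shared test times, adjusts for the number of tests, or treats onset as known only to within a testing interval.

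**The concern.** The chance of seeing at least one abnormal value, and the worst grade seen, both rise with the number of tests. Time to onset, as recorded, is time to the first test that shows the abnormality. If one randomised group is tested twice as often, some of the difference between the groups is detection.

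Here the detection difference runs in the direction a reader would expect from the drug. Cohort A continues nivolumab and Cohort B has stopped, so extra abnormalities in A would be read as the cost of continued treatment. Describing the safety of two treatment durations is a stated exploratory purpose of the randomisation (Section 1.1.1), and this artefact would blur it.

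**Working it through.** **1. The plan's own figure.** The documents give no figure for the laboratory contrast. The nearest is the number expected to be randomised, 99 to 322 (Section 8.1.1). The proportion is 10/37 = 0.270, with standard error √(0.270 × 0.730 / 37) = 0.073. The 95% interval 0.270 ± 1.96 × 0.073 is 12.7% to 41.3%. Multiplied by 780 this gives 99.1 and 322.1, so the figure reproduces. At 1:1 that is about 50 to 161 subjects per cohort.

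**2. Scheduled tests in the 52 weeks after randomisation**, with A on drug and B off it throughout (52 / interval, intervals from Table 5.1-2):
- Routine tests: 52/2 = 26 in A, 52/4 = 13 in B.
- TSH: 52/6 = 8.7 in A, 52/12 = 4.3 in B, if B uses the permitted interval.

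**3. Recorded incidence under equal true risk.** Assume the same probability q of an abnormal result at each test in both cohorts, independent between tests. This suits abnormalities that are short relative to the interval. P(at least one in k tests) = 1 − (1 − q)^k. With 26 and 13 tests the ratio A:B equals 1 + (1 − q)^13, so it cannot exceed 2. The documents do not give q; a range is shown.

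| Assumed q | A (26 tests) | B (13 tests) | Ratio |
|---|---|---|---|
| 0.25% | 6.3% | 3.2% | 1.97 |
| 0.5% | 12.2% | 6.3% | 1.94 |
| 1% | 23.0% | 12.2% | 1.88 |
| 2% | 40.9% | 23.1% | 1.77 |
| 5% | 73.6% | 48.7% | 1.51 |

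For TSH with 8 against 4 whole tests and q = 1%: 7.7% against 3.9%, ratio 1.96.

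**4. Counting from first dose, as Section 8.4.4.1 does for onset.** Both cohorts share a first year of 26 routine tests, so two years give 52 tests against 39. At q = 1%: 1 − 0.99^52 = 40.7% against 1 − 0.99^39 = 32.4%, ratio 1.26. At q = 0.25% the ratio is 1.31, and at 5% it is 1.08.

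**5. Dependence on how long an abnormality lasts.** For an episode of fixed length d and testing interval I, the chance that a test falls within it is min(1, d/I).
- A 2-week episode on routine tests: 100% in A, 50% in B.
- A 6-week TSH episode: 100% in A, 50% in B.
- An episode of at least 4 weeks (12 for TSH): found in both.

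If durations are exponential with mean m, the chance is (m/I)(1 − e^(−I/m)). For m = 2, 4 and 8 weeks the routine-test ratios A:B are 0.632/0.432 = 1.46, 0.787/0.632 = 1.24 and 0.885/0.787 = 1.12.

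**6. Time to onset of persistent abnormalities.** The mean delay to detection is half the interval: 1 week in A against 2 in B for routine tests, and 3 against 6 for TSH.

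**7. On a common grid.** With only the shared 4-weekly times (12-weekly for TSH), each cohort has 13 routine and about 4 TSH tests per 52 weeks. The expected ratio under equal true risk is 1.0.

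**The case against.** The strongest reply is that this is a caveat on an exploratory display, and that several stronger readings fail.

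- A reader might infer a planned comparison of the cohorts by worst grade. The documents do not say that. The worst-grade sentence names all treated subjects only and reaches the cohorts only through Section 8.2 and the paragraph that follows it. The cohort summaries are descriptive, with no test, alpha or power. This stands.
- A reader might infer a doubling. Two is the ceiling for data after randomisation. The plan defines no post-randomisation window, and onset runs from first dose, so the shared first year dilutes the effect. Longer episodes dilute it further. This stands.
- A reader might infer that Cohort A is always favoured in detection. Under Table 5.1-3, a Cohort A subject who stops treatment has laboratory tests only at the two follow-up visits, about 30 and 100 days after the last dose. Section 3.5 keeps Cohort B on the on-study visits, and retreatment restores two-weekly tests. Part of the imbalance therefore runs the other way. This stands.
- A reader might infer that the main endpoints are touched. They are defined on high-grade select adverse events, and the primary summary pools all treated subjects. The point does not extend to them.

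The small cohorts also matter. At n = 100 and a 5% rate, Table 8.1-1 gives an interval of 1.64% to 11.28%, so a factor of 1.26 would be hard to see. That limits the consequence but does not remove the bias, which more subjects would not cure.

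A simple 4-weekly grid is also open to challenge. Cohort A tests follow dosing and move with dose delays, so shared calendar times do not exist until visit windows are defined. The fix has to supply them.

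**Conclusion.** The point holds in a limited form. While A is on nivolumab and B is off it, scheduled testing differs by a factor of two (for TSH, if the permitted interval is used), and the planned by-cohort laboratory summaries ignore this. With equal true risk, A would show more short-lived abnormalities and somewhat earlier onset of persistent ones. The ratio in recorded incidence is at most about 2 after randomisation, about 1.26 over two years at q = 1%, and close to 1 for long-lasting abnormalities.

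These sizes rest on assumed per-test probabilities and episode durations, on subjects remaining on or off drug for the period counted, and on no unscheduled tests. The direction during the on-drug versus off-drug period does not depend on the values chosen; over the whole of follow-up the net direction is uncertain. The matter is minor: it concerns the reading of an exploratory table and does not call the different monitoring schedules into question.

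**What to change.** Add one exploratory laboratory summary of Cohort A against Cohort B to Section 8.4.4.1, defined as follows:

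- Count from randomisation.
- Include each subject only up to treatment discontinuation (A) or retreatment (B). For a Cohort B subject who is not retreated, stop at the move to the Table 5.1-3 follow-up visits.
- Use scheduled results only, mapped by pre-specified visit windows to a 4-weekly grid (12-weekly for TSH). Take one result per window, the one nearest the target date. Taking the worst in the window would bring the imbalance back.
- Report incidence, worst grade and time to onset on that grid, with the number of grid results contributed by each cohort, since the two windows may differ in length.
- Keep the all-tests summary alongside, with a note on the different schedules.

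The cost is one extra table from data already collected. About half of Cohort A's scheduled tests after week 52 go unused in that table, though they remain in the all-tests summary. The windows also end for different reasons in the two cohorts, so the table stays descriptive. No visit, test or monitoring rule changes.

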4.1 Study Treatments

Nivolumab 100 mg (10 mg/mL) will be packaged in an open-label fashion. Ten BMS-936558 (nivolumab), 10 mL vials will be packaged within a carton (see [Table 4.1-1](#)), and are not subject or treatment arm specific. Vial assignments by subject will be made through the IVRS (interactive voice response system) to track usage and resupply.

As described in [Section 3.1](#), nivolumab will be dosed intravenously at 3 mg/kg every two weeks. After 1 year (52 weeks) of treatment the subjects who are still on the study and benefiting from the therapy will be randomized (1:1) via IVRS to one of the two cohorts, Cohort A or Cohort B.

Subjects randomized to Cohort A will be treated until disease progression, unacceptable toxicity, or withdrawal of informed consent. Subjects randomized to Cohort B will discontinue treatment at 1 year (52 weeks). Subjects in Cohort B will remain on the study and will follow all study assessments [REDACTED]. At progression, subjects in Cohort B may receive retreatment [REDACTED].

Subjects who are retreated can continue until progression, unacceptable toxicity, or withdrawal of informed consent. Study treatment can continue beyond initial investigator assessed progression, as specified in criteria presented in [Section 4.3.4 Treatment Beyond Disease Progression](#).

Table 4.1-1: Product Description

Product Description and Dosage Form	Potency	Primary Packaging (Volume)/ Label Type	Secondary Packaging (Qty) /Label Type	Appearance	Storage Conditions (per label)
BMS-936558-01 Solution for Injection	100 mg (10 mg/mL)	10 mL vial/ Open-label	10 vials per carton/ Open-label	Clear to opalescent, colorless to pale yellow liquid. May contain particles.	2 to 8° C. Protect from light, shaking, and freezing.

NOTE: Medications used to treat BMS-936558 (nivolumab)-related infusion reactions are (eg, diphenhydramine, acetaminophen/paracetamol, corticosteroids) considered NIMPs (noninvestigational products) and will not be provided by the sponsor. These will be obtained by the investigational sites as marketed product, which should be stored in accordance to the package insert. For further details related to these medications and BMS-936558 (nivolumab)-related infusion reactions, please see [Section 4.3.6](#).

4.1.1 *Investigational Product*

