4.4 Blinding/Unblinding

Not applicable.

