Radiographic tumor assessments				X	
At Week #9 (the 9th week on study with C1D1 week counted as week #1) \pm 5 days and every 8 weeks (\pm 5 days) thereafter up to 24 months from first dose then every 12 weeks (\pm 5 days) regardless of dosing schedule, until documented disease progression or discontinuation of study therapy in subjects receiving nivolumab beyond progression.
 
Assessments should include all areas that are being monitored and new areas if clinically indicated (with contrast unless contraindicated). Follow RECIST 1.1 criteria.
 
Subjects with a history of brain metastasis (BM) should have surveillance MRI approximately every 12 weeks, or sooner if clinically indicated.
 
After 24 months of treatment, the frequency of surveillance brain MRI or CT scans will be every 6 months or earlier, if clinically indicated, for subjects with known brain metastases.

Table 5.1-2: On-Study Procedural Outline (CA209153)

Procedure	C1D1 (Cycle 1 Day 1)	Each Cycle (Every 2 weeks) on Day 1	Every 3 Cycles (Every 6 weeks) on Day 1	Every 4 Cycles (Every 8 weeks) on Day 1	Notes
Randomization		At 1 year (52 weeks)			Subjects that are still on study and benefiting from treatment will be randomized 1:1 to Cohort A or B.

Table 5.1-2: On-Study Procedural Outline (CA209153)

Procedure	C1D1 (Cycle 1 Day 1)	Each Cycle (Every 2 weeks) on Day 1	Every 3 Cycles (Every 6 weeks) on Day 1	Every 4 Cycles (Every 8 weeks) on Day 1	Notes
Administration of nivolumab (BMS-936558) 3 mg/kg	X	X			
All subjects start treatment on C1D1 and continue treatment every 2 weeks until disease progression, unacceptable toxicity, or withdrawal of informed consent. At 1 year (52 weeks) all subjects that remain on treatment will be randomized to Arm A or Arm B.
 
Cohort A subjects will continue treated until disease progression, unacceptable toxicity, or withdrawal of informed consent.
 
Cohort B subjects will discontinue treatment at 1 year (52 weeks \pm 2 weeks). Upon progression, subjects can be retreated until progression, unacceptable toxicity, or withdrawal of informed consent.
 
Treatment for all subjects can continue beyond initial investigator-assessed progression as specified in Section 4.3.4. Drug administration is $+/-$ 3 days but no less than 12 days from previous dose. Study drug infusion start and stop times will be recorded. .

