8.3.3 Exploratory Endpoint(s)

Safety and tolerability will be measured by the incidence of all adverse events, serious adverse events, deaths and laboratory abnormalities. Adverse event assessments and laboratory tests will be performed at baseline, and continuously throughout the study at the beginning of each subsequent cycle.

Efficacy data will be assessed by measuring OS, DOR, ORR and PFS. These endpoints are defined as follows:

- OS is defined as the time from first dosing date to the date of death. A subject who has not died will be censored at last known date alive. OS will be followed continuously while subjects are on the treatment and every 3 months via in-person or phone contact after subjects discontinue the study drug.
- DOR is defined as the time from first confirmed response (CR or PR) to the date of the initial objectively documented tumor progression as determined using RECIST 1.1 criteria or death due to any cause, whichever occurs first. For subjects who neither progress nor die, the DOR will be censored on the date of their last evaluable tumor assessment. DOR will only be evaluated in subjects with objective response of CR or PR.
- Objective response rate (ORR) is defined as the number and percentage of subjects with a best overall response (BOR) of confirmed complete response (CR) or partial response (PR).

Best overall response (BOR) is defined as the best response designation, recorded between the date of first dose and the date of the initial objectively documented tumor progression per RECIST v1.1 or the date of subsequent therapy, whichever occurs first. For subjects without documented progression or subsequent therapy, all available response designations will contribute to the BOR determination.

- Progression-free survival (PFS) is defined as the time from first dosing date to the date of the first documented tumor progression, as determined by investigators (per RECIST v1.1), or death due to any cause, whichever occurs first. Subjects who die without a reported prior progression will be considered to have progressed on the date of their death. Subjects who did not progress or die will be censored on the date of their last evaluable tumor assessment. Subjects who did not have any on study tumor assessments and did not die will be censored on the first dosing date.

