4.4 Special notes on response assessment

When nodal disease is included in the sum of target lesions and the nodes decrease to 'normal' size (< 10 mm), they may still have a measurement reported on scans. This measurement should be recorded even though the nodes are normal in order not to overstate progression should it be based on increase in size of the nodes. As noted earlier, this means that patients with CR may not have a total sum of 'zero' on the case report form (CRF).

Patients with a global deterioration of health status requiring discontinuation of treatment without objective evidence of disease progression at that time should be reported as 'symptomatic

deterioration'. Every effort should be made to document objective progression even after discontinuation of treatment. Symptomatic deterioration is not a descriptor of an objective response: it is a reason for stopping study therapy. The objective response status of such patients is to be determined by evaluation of target and non-target disease as shown in [Appendix Table 1](#) and [Table 2](#).

For equivocal findings of progression (eg, very small and uncertain new lesions; cystic changes or necrosis in existing lesions), treatment may continue until the next scheduled assessment. If at the next scheduled assessment, progression is confirmed, the date of progression should be the earlier date when progression was suspected.

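### Investigator-assessed PFS and DOR by cohort are at risk of bias, probably against stopping, because in this open-label trial a progression call reopens access to drug only in Cohort B

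*Combined protocol and SAP*

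**What the plan says.** Table 5.1-2 sets the randomized step: "Subjects that are still on study and benefiting from treatment will be randomized 1:1 to Cohort A or B". Section 4.1 states that "Nivolumab 100 mg (10 mg/mL) will be packaged in an open-label fashion", Section 4.4 ("Blinding/Unblinding") is marked not applicable, and so is Section 5.9 on central assessments.

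Section 8.3.3 ends PFS at "the date of the first documented tumor progression, as determined by investigators (per RECIST v1.1), or death due to any cause". The DOR definition there names no assessor, but Section 5.4.1 gives the RECIST reading to the investigator and uses that reading to guide treatment. With no central read, DOR rests on the same person.

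A progression call has different consequences in the two cohorts:

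- **Cohort B.** Section 3.5 keeps the subject off drug until progression makes retreatment possible. Table 5.1-2 puts it as "Upon progression, subjects can be retreated until progression, unacceptable toxicity, or withdrawal of informed consent".
- **Cohort A.** The subject is on drug already. The call ends treatment unless the conditions of Section 4.3.4 are met, which include new written consent and a discussion with the medical monitor. Table 5.1-2 adds: "Treatment for all subjects can continue beyond initial investigator-assessed progression as specified in Section 4.3.4".

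Section 8.4.4.2 summarizes PFS and DOR for Cohorts A and B by Kaplan-Meier methods with confidence intervals. The visible text has no check on how progression was called.

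**The concern.** The person who decides whether a scan shows progression knows the cohort, and in Cohort B that decision is the only visible route back to nivolumab. If a borderline finding is called more readily in Cohort B, stopping will show shorter PFS and DOR even when the tumors behave identically.

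This is the trial's only randomized comparison. Section 1.1.2.1 intends it to show how treatment duration affects the durability of response and whether other schedules deserve study. Section 8.5 foresees data cuts for publication. Once a Cohort B subject restarts drug, later scans are taken on treatment and can no longer show that the call was premature.

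**Working it through.** **1. The plan's own figure.** The only number given for the cohort step is 99 to 322 randomized (Section 8.1.1). From 10/37 = 0.270, the Wald interval 0.270 ± 1.96 × √(0.270 × 0.730 / 37) is 12.7% to 41.3%. Then 780 × 0.127 = 99.06 and 780 × 0.413 = 322.14, so the figure reproduces. The same rates on the current total of 1280 give 163 to 529. The plan states no test, hazard ratio, power or event count for A versus B, so none can be reproduced.

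**2. Which mechanism survives the RECIST text.** Appendix 1, Section 4.4, says that for equivocal findings "treatment may continue until the next scheduled assessment". The next sentence dates a confirmed progression back to the scan where it was suspected. Appendix 1, Section 3.3, does the same for equivocal new lesions. Waiting in Cohort A therefore does not postpone a confirmed event. Two routes remain: (a) Cohort B findings called as progression that would never have been confirmed, and (b) true Cohort B progressions called one scan early. Scan timing does not contribute, because Table 5.1-2 sets it regardless of dosing.

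**3. Size under assumptions.** None of the following is in the documents: no true A/B difference, and exponential time from randomization to progression with medians of 6, 12 or 24 months. Scans are 8-weekly to week 48 after randomization and 12-weekly afterwards, with 204 weeks of follow-up and 40,000 simulated subjects per arm. The standard error of the hazard ratio is about 0.01, and runs with no distortion gave 1.01 to 1.02, so the second decimal is approximate.

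| Assumed distortion in Cohort B | Apparent HR, B versus A |
|---|---|
| 10% of true progressions one scan early | 1.01–1.03 |
| 25% one scan early | 1.03–1.05 |
| 50% one scan early | 1.07–1.10 |
| 1% false calls per scan | 1.04–1.13 |
| 3% false calls per scan | 1.13–1.45 |

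A second simulation used medians of 12 to 24 months and the first scan 5 weeks after randomization (study week 57). It gave 1.08–1.15 at 1% and 1.23–1.45 at 3%. Together the ranges are about 1.04–1.15 and 1.13–1.45.

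Hand check of the false-call rows. Let p = 1 − exp(−λΔ) be the chance of true progression between scans, with λ = ln 2 / median, and let q be the false-call rate. The per-scan ratio is 1 + q(1 − p)/p. For a 24-month median (at 4.345 weeks per month) λ = 0.00665 per week, so p = 0.0518 for Δ = 8 weeks and 0.0767 for Δ = 12 weeks. At q = 3% the ratio is 1.55 and 1.36, which bracket the simulated 1.45. For a 12-month median, p = 0.1009 and 0.1475. At q = 3% the ratio is 1.27 and 1.17, which bracket the simulated 1.23.

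**4. What these rates imply.** The share of Cohort B events that are false is about 1 − 1/HR. For medians of 12 to 24 months this is 1 − 1/1.07 to 1 − 1/1.15, or 7% to 13%, at q = 1%. At q = 3% it is 1 − 1/1.23 to 1 − 1/1.45, or 19% to 31%. The 3% case is therefore a strong assumption. On the plan's own scale, a fraction f called one scan early moves the mean recorded time by about f × Δ, from 0.10 × 8 = 0.8 weeks to 0.50 × 12 = 6 weeks.

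**5. Against sampling error.** With d events and 1:1 allocation, the 95% interval for a hazard ratio extends by a factor exp(1.96 × 2/√d) either way. If 50% to 80% have events (assumed), 99 to 322 randomized gives d = 49.5 to 257.6 and factors of 1.75 to 1.28. For 163 to 529 randomized, d = 81.5 to 423.2 and the factors are 1.54 to 1.21. Most of the distortions above lie inside that noise, but unlike noise they do not shrink as numbers grow.

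**The case against.** The strongest reply is that a one-sided incentive is not a demonstrated bias. A reader might infer from the design that the cohort results are biased against stopping. The documents do not show that. Appendix 1 constrains calls equally in both cohorts: a numeric target rule, new lesions that must be unequivocal, and a modest non-target increase usually not enough. This stands, and only a risk can be claimed.

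A reader might also infer that Cohort A events are recorded late because equivocal findings can wait. The back-dating rule rules that out once progression is confirmed.

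Section 4.3.4 lets Cohort A continue after progression, which weakens any motive to delay a call there. It does not create a matching gain, since only Cohort B regains access.

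The comparison is exploratory and descriptive (Section 1.1.1), and the primary and secondary objectives are safety, so no confirmatory conclusion is at stake. This limits the weight of the point but does not remove it.

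The assumed rates have no source in the documents, and the hazard ratio is only a yardstick. Finally, part of the retreatment text is redacted (Synopsis, Study Design; Section 4.1). It may set conditions beyond a bare investigator call, and this cannot be verified.

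**Conclusion.** The point holds as a risk of bias, probably against stopping, in investigator-assessed PFS and DOR by cohort. It rests on four visible facts: open-label treatment, no central read, one reading that both defines progression and guides treatment, and renewed access to drug through that reading in Cohort B alone. The size is unknown. It is negligible to small if true progressions are only called early (about 1.01 to 1.10). It becomes material only if false calls are frequent (about 1.04 to 1.15 at 1% per scan, 1.13 to 1.45 at 3%). It does not touch the safety objectives. The change is worth making because it uses data already recorded and makes the only randomized comparison easier to interpret.

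**What to change.** In Section 8.4.4.2, for all randomized subjects:

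1. Tabulate by cohort the basis of each investigator progression: target sum, non-target (including palliative radiotherapy counted as progression under Section 3.4.3), new lesion, or clinical only. Show whether each target-based call met the 20% and 5 mm rule, and the share of calls made at unscheduled scans.
2. Beside the investigator version, present a sensitivity PFS and DOR from recorded lesion data under full RECIST 1.1: target rule by program, recorded unequivocal non-target progression, recorded new lesions, and death. Omitting the non-target component would drop genuine events. Apply one rule in both cohorts and use only scans up to and including the investigator's call. The cut-off matters because retreated Cohort B subjects stay on the on-study schedule (Section 3.5), whereas Table 5.1-3 requires follow-up scans only for subjects who stop for reasons other than progression. Using later scans would let Cohort B accrue PFS on resumed drug. Show calls that the recorded data do not support both as events and as censored at that scan.
3. Report disagreement between the versions as a limitation of the cohort comparison. Do not make agreement a formal decision rule.

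The cost is programming and one or two tables, with no new scans, no central reader and no change in management. The check is partial: measurements and non-target or new-lesion calls still come from unblinded readers, and censoring unsupported calls may be informative.
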